9.5.2.2. SAS Code for the Secondary/Exploratory Efficacy Endpoints

9.5.2.2.1. Analysis of Covariance (ANCOVA)

For some secondary endpoints, an ANCOVA model will be used to compare the 2 treatment groups. The basic SAS code for this analysis is given by:

```
proc glm data = adef;  
class trt01p intub;  
model aval = trt01p age intub / solution;
```

```
lsmeans trt01p / cl diff stderr;  
run;
```

where aval is the number of days.

Missing data will be imputed using a multiple imputation approach assuming the data are MAR and using a regression model. The basic SAS code for this is:

```
Proc mi data=adeff out=outmi seed=1306528 nimpute=pctmissing round=. . . . 1 maximum=. . .  
.. 29 minimum=. . . . 1;  
class trt01p intub sex comorbid;  
var trt01p intub sex age comorbid aval;  
monotone reg(aval = trt01p intub sex age comorbid / details);  
run;
```

If an imputed value for a patient is less than the observed number of days until dropout, then the observed number will be used. The imputed data sets will then be analyzed by imputation using the ANCOVA method described above and the PROC MIANALYZE procedure will be used to generate valid statistical inferences about these parameters. The basic SAS code for this is:

```
Proc mianalyze data=parameterestimates;  
modeffects estimate;  
stderr stderr;  
run;
```

A sensitivity analysis will use a delta-adjustment tipping point approach where the missing data for patients randomized to ravulizumab + BSC group are imputed by shifting the number of days for the observed patients downward by delta. For each value of delta, the treatment effect will be determined, and the value of delta for which the nominal 2-sided p-value crosses 0.05 will be considered as the ‘tipping point’ in the sense that the positive conclusion drawn from the primary analysis is reversed. The basic SAS code for this is:

```
Proc mi data=adeff out=outmi seed=1306528 nimpute=pctmissing round=. . . . 1 maximum=. . .  
.. 29 minimum=. . . . 1;  
class trt01p intub sex comorbid;  
var trt01p intub sex age comorbid aval;  
monotone reg(aval = trt01p intub sex age comorbid / details);  
mmar adjust (aval / shift=delta adjustobs=(trt01p='Ravulizumab + BSC'));  
run;
```

where delta is the shift parameter for the imputed values of days for patients randomized to ravulizumab + BSC group.

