5.1.2.1. Mechanical Ventilation

The number of days free of mechanical ventilation is defined as the total number of days from Day 1 to Day 29 without invasive or non-invasive mechanical ventilation.

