7.2.2. Secondary Analyses

A closed testing procedure will be applied to control the type I error for the analyses of the primary and secondary endpoints at Day 29. If the primary endpoint is statistically significant in favor of ravulizumab, the secondary endpoints will be evaluated according to the following rank order:

1. Number of days free of mechanical ventilation at Day 29,
2. Duration of ICU stay at Day 29,
3. Change from baseline in SOFA score at Day 29,
4. Change from baseline in SpO₂/FiO₂ at Day 29,
5. Duration of hospitalization at Day 29.

The hypothesis testing will proceed from highest rank (#1) the number of days free of mechanical ventilation at Day 29 to the lowest rank (#5) duration of hospitalization at Day 29, and if statistical significance is not achieved at an endpoint ($p \geq 0.05$), then endpoints of lower rank will not be considered to be statistically significant. Confidence intervals and p-values will be presented for all secondary efficacy endpoints for descriptive purposes, regardless of the outcome of the closed testing procedure.

An additional secondary endpoint will be assessed beyond Day 29 regardless of the results of the closed testing procedure: Survival (based on all-cause mortality) at Day 60 and Day 90.

The PPS will be used in a sensitivity analysis for all secondary efficacy endpoints.

7.2.2.1. Number of Days Free of Mechanical Ventilation at Day 29

The number of days free of mechanical ventilation at Day 29 will be summarized by treatment group for all patients and by mortality. The number of days free of mechanical ventilation at Day 29 will be compared between treatment groups using an analysis of covariance (ANCOVA), adjusting for age and the randomization stratification factor, among survivors (ie, the number of days alive and free of mechanical ventilation).

Missing data will be imputed using a multiple imputation approach assuming the data are MAR and using a regression model with covariates for treatment group, the randomization stratification factor, age, sex and presence of a pre-existing condition at baseline (diabetes mellitus, obesity, respiratory condition, and/or coronary artery disease). Sensitivity analyses will include:

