- Worst-case scenario: missing days up to Day 29 for patients randomized to ravulizumab + BSC group will be considered as alive and not free of mechanical ventilation and missing days for patients randomized to BSC group will be considered as alive and free of mechanical ventilation for the remaining days up to Day 29
- All available data: no imputation of missing data
- Best-case scenario: missing days up to Day 29 for patients randomized to ravulizumab + BSC group will be considered as alive and free of mechanical ventilation and missing days for patients randomized to BSC group will be considered as alive and not free of mechanical ventilation for the remaining days up to Day 29
- Delta-adjustment tipping point analysis ([O’Kelly and Ratitch, 2014](#)): missing data for patients randomized to ravulizumab + BSC group are imputed by shifting the number of days alive and free for the observed patients downward by delta until any positive conclusion drawn from the primary analysis is reversed; refer to [Appendix 9.5.2.2.1](#) for additional details

7.2.2.2. Duration of ICU Stay at Day 29

The duration of ICU Stay at Day 29 will be summarized by treatment group for all patients and by mortality. Duration of ICU stay at Day 29 will be compared between the 2 treatment groups using an ANCOVA, adjusting for age and randomization stratification factor, among survivors (ie, the number of days alive and not in the ICU). Missing data will be handled as described for number of days free of mechanical ventilation at Day 29. The proportion of patients discharged

from the ICU will also be summarized and compared between the 2 treatment groups in a similar manner as the primary analysis of the primary endpoint.

7.2.2.3. Change from Baseline in SOFA Score at Day 29

Changes in SOFA score from Day 1 to Day 29 will be summarized by treatment group and study visit for all patients and by mortality.

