9.4.5. Definition of Durations

9.4.5.1. Number of Days Free of Mechanical Ventilation at Day 29

The number of days free of mechanical ventilation at Day 29 among survivors (ie, the number of days alive and free of mechanical ventilation) will be defined as:

Number of days alive – Number of days on mechanical ventilation, where

- Number of days alive = Earliest of Day 29 Visit Date or Disposition Date (for death) – Date of Day 1 + 1; set to 29 if > 29.

- Number of days on mechanical ventilation = sum of total number of days with mechanical ventilation from Date of Day 1 to Date of Day 29 Visit or Disposition Date (for death) ; set to 29 if > 29.

9.4.5.2. Duration of ICU Stay at Day 29

The duration of ICU stay at Day 29 among survivors (ie, the number of days alive and not in the ICU) will be defined as:

Number of days alive – Number of days in ICU, where

- Number of days alive is as defined in [Section 9.4.5.1](#).
- Number of days in ICU = sum of total number of days in ICU from Date of Day 1 to Earliest of Date of Day 29 Visit or Disposition Date (for death); set to 29 if > 29.

Number of days from first ICU date to Day 1 = Date of Day 1 – Date of first ICU entry; set to zero if negative.

9.4.5.3. Duration of Hospitalization at Day 29

The duration of hospitalization at Day 29 among survivors (ie, the number of days alive and not hospitalized) will be defined as:

Number of days alive – Number of days in hospital, where

- Number of days alive is as defined in [Section 9.4.5.1](#).
- Number of days in hospital = sum of total number of days in hospital from Date of Day 1 to Earliest of Date of Day 29 Visit or Disposition Date (for death); set to 29 if > 29.

Number of days from hospitalization to first dose date = Date of Day 1 – Date of hospitalization.

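### The imputation for three day-count secondaries (ranks 1, 2 and 5) ignores each patient's status and days observed before dropout, so imputed counts can contradict the record

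*SAP*

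**What the plan says.** SAP 5.1.2.1 defines the first-ranked secondary as the "total number of days from Day 1 to Day 29 without invasive or non-invasive mechanical ventilation". SAP 9.4.5.1 computes it as days alive minus the "sum of total number of days with mechanical ventilation from Date of Day 1" to the Day 29 visit or death. SAP 9.4.5.2 and 9.4.5.3 do the same for ICU and hospital days.

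For missing data, SAP 7.2.2.1 specifies multiple imputation under MAR "using a regression model with covariates for treatment group, the randomization stratification factor, age, sex and presence of a pre-existing condition at baseline". The code in 9.5.2.2.1 matches: "monotone reg(aval = trt01p intub sex age comorbid / details". The code also sets a rounding unit, a minimum of 1 and a maximum of 29. These are garbled in the text but are most naturally read as applying to the day count. One sentence then corrects individual values: "If an imputed value for a patient is less than the observed number of days until dropout, then the observed number will be used". No patient-level upper limit is stated in 7.2.2.1, 9.4.5 or 9.5.2.2.1.

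SAP 7.2.2.2 and 7.2.2.5 carry the rule to ICU and hospital days: "Missing data will be handled as described for number of days free of mechanical ventilation at Day 29". The tipping-point run, in which missing values are "imputed by shifting the number of days for the observed patients downward by delta", uses the same bounds. The best-case run works differently: "missing days up to Day 29 for patients randomized to ravulizumab + BSC group will be considered as alive and free of mechanical ventilation". It fills only the missing days and keeps the observed ones.

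**The concern.** A patient who leaves on Day 20 has 20 days of known status and 9 unknown days. The plan discards the known part and redraws all 29 days from baseline characteristics. The draw is then checked from below only. Two patients with the same baseline profile, one ventilated throughout and one off the ventilator since Day 3, get draws from the same distribution, although their possible final counts barely overlap.

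This is the main analysis of three of the five endpoints in the ordered testing sequence, and rank 1 controls access to the other four. The treatment comparison would be at risk if dropouts in the two arms were in different states when they left, because the imputation cannot tell those states apart.

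**Working it through.** **Inputs from the documents:** 29-day window; count = days alive minus days not free; code bounds read as 1 and 29; floor as quoted; 180 and 90 patients randomized; nonevaluable allowance of 10% (1 − 243/270). The documents give no mean, SD or missing rate for these endpoints, so there is no figure of the plan's own to reproduce.

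**1. Feasible range.** For a patient last seen alive on day d, with f free days and v = d − f not-free days, the final count lies in [f, 29 − v]. With the floor read as observed free days, the plan permits [max(f, 1), 29]. It therefore allows v impossible values above the true maximum.

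| Observed | Feasible | Permitted by plan |
|---|---|---|
| ventilated Days 1–10 | 0–19 | 1–29 |
| ventilated Days 1–20 | 0–9 | 1–29 |
| ventilated Days 1–22 | 0–7 | 1–29 |

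Protocol 5.1 (criteria 2 and 4) requires hospitalization and mechanical ventilation at entry. Anyone still ventilated or in hospital on Day 1 can reach at most 28 on that count, so a common maximum of 29 is too high even then.

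**2. Against the SAP's own extremes.** The best-case fill for a ravulizumab patient gives f + (29 − d) = 29 − v. The main imputation can exceed it by up to 29 − (29 − v) = v days.

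**3. The floor.** If it means days on study, the floor is d. For a patient ventilated throughout, the ceiling is 29 − d. From d = 15 the floor (15) exceeds the ceiling (14), and every permitted value is impossible.

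**4. Size, all inputs assumed.** Base case for ventilation: 45% never free, the rest free from a day uniform on 2–29, dropout uniform on Days 2–28, no return to ventilation. Dropout is unrelated to outcome given status and day. Completers' mean = 0.55 × 14.5 = 8.0. Variance = 0.55 × 275.5 − 8.0² ≈ 88, so SD is 9.4. Imputed values are rounded normal draws with that mean and SD, redrawn to 1–29, then floored at observed free days.

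| Group | Imputed mean | True mean |
|---|---|---|
| still ventilated at dropout | 11.1 | 3.7 |
| already off | 14.2 | 19.3 |
| all dropouts | 12.0 | 8.0 |

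Unbounded draws average 8.0. The 1–29 bounds lift this to 11.1 and the floor to 12.0. Of the imputed values, 28% exceed the patient's maximum; for a patient ventilated through Day 20 it is 55%. Across 12 variants (30, 45 or 60% never free; even or early liberation; 20% or 80% of dropouts already off) the error per imputed patient runs from −3.9 to +6.6 days. ICU days (50–60% never out) show the same pattern: 8.5–9.4 against 2.6–3.4 if still in, 11.4–12.1 against 16.6 if out. So do hospital days (60–75% never out): 5.4–6.8 against 1.5–2.6, and 8.3–9.1 against 13.3.

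**5. Effect on the treatment difference (ventilation).** Standard error = 9.4 × √(1/180 + 1/90) = 1.2.

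| Dropout pattern | 2% missing | 10% missing |
|---|---|---|
| same in both arms (true difference 2.2–4.4 days) | 0.01–0.03 day | 0.06–0.15 day |
| 80% v 20% already off | 0.14–0.17 day | 0.70–0.84 day |

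In the first row the difference shrinks. In the second it moves either way, depending on which arm has more dropouts already off.

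**6. Adding only a ceiling.** With the same dropout pattern in both arms and 10% missing, the error in the difference changes from 0.09 to 0.10 day (30 v 45% never free), 0.06 to 0.09 (45 v 60%) and 0.15 to 0.19 (30 v 60%). It grows slightly.

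**The case against.** The strongest reply is that multiple imputation is judged by the treatment estimate, not by whether each imputed value is plausible. That stands. About half of the unbounded draws in step 4 are also infeasible, yet they average the true 8.0. A reader might infer from the 28% or 55% figures that the estimate is biased by a similar amount; those percentages do not measure bias. A reader might also infer that the missing ceiling is the cause and that supplying one is the cure. Step 6 shows otherwise: the errors by state come from leaving status and day at dropout out of the model.

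It is also fair that little may be missing. Deaths have a defined count (SAP 9.4.5), Protocol 8.4.10 and 8.4.12 provide a Day 29 call after early discharge or termination, and Protocol 7.2 expects withdrawal to be uncommon. The best-case and worst-case runs already respect each patient's range and would expose a result that hangs on the imputation. This limits the size but does not remove the fault: the call records health status on Day 29, and the protocol does not say that it recovers the day-by-day history.

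Finally, the code is described as basic, its bounds are garbled, and the floor most naturally means free days. The overall upward shift in step 4 does depend on reading the bounds as 1–29. The omission of status and observed days does not, because the covariate list and the floor are stated in the SAP's text.

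**Conclusion.** The point holds as a minor one. The main imputation for ranks 1, 2 and 5 ignores what was observed before dropout, can return counts that contradict it, and can exceed the SAP's own best case. The floor needs a definition. If the bounds are 1–29 for the count, the valid score 0 can never be imputed.

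The impossible values follow from the definitions alone. The sizes rest on assumed ventilation, ICU, discharge and dropout patterns. With like dropout in both arms, the effect on the treatment difference is roughly 5–12% of a standard error at 10% missing (0.06/1.2 to 0.15/1.2), and 10% is only an upper illustration taken from the nonevaluable allowance. Dropout that differs by state between arms could raise it to 0.70–0.84 day, but nothing in the documents suggests such a split. A reader might infer that the rule favours ravulizumab; the documents support no direction. Primary survival at Day 29 is not touched.

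**What to change.** In SAP 9.5.2.2.1, with matching text in 7.2.2.1:

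- Keep the days observed up to dropout, impute only the remaining days (0 to 29 minus dropout day), and add the two.
- Put status and day at dropout into the imputation model. Preferably draw the remaining days from observed values of patients with the same status on that day, pooling nearby days where few. In the base case this returned 3.7 and 19.3 days, equal to the truth. Normal draws of the remaining days cut to bounds gave 5.3 against 3.7 for those still ventilated.
- Define the floor as free days already observed, and allow 0.
- Use the same limits in the tipping-point run and for all three endpoints.

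Do not simply add a ceiling or clamp whole-count draws. That removes impossible values without addressing the omitted status, and a ceiling alone does not reduce the error in the treatment difference.

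The cost is a few lines of text and code. No new data are needed, since the best-case and worst-case runs already require each patient's observed and missing days. The sample size is unchanged.

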9.5.2.2.2. Mixed Model for Repeated Measures (MMRM) Analysis

For some secondary endpoints, the analysis of changes over time involves an MMRM analysis. The basic SAS code for this analysis is given by:

```
proc mixed data = adeff method = reml;
  class subjid avisit trt01p intub;
  model chg = trt01p avisit trt01p*avisit base age intub / ddfm = kr solution;
  repeated avisit / type=un subject=subjid;
  lsmeans trt01p*avisit / cl diff;
  where 1 < avisitn;
run;
```

where trt01p is a variable that indicates the patient's randomized treatment group, subjid is the patient variable, avisit is the study day variable (0 representing Day 1), base is the value at baseline, age is patient age on Day 1, chg is the change from baseline at a particular visit, and intub is the randomization stratification factor.

The following illustrates the sensitivity analysis for missing data using the control-based approach, where for patients who discontinued treatment, responses after treatment discontinuation for both treatment groups will be imputed with multiple imputation methodology based on the response for BSC alone patients. Markov Chain Monte Carlo (MCMC) imputation method will be used to fill in the intermittent missing values under the assumption of MAR and generate a monotone pattern. Subsequently, multiple imputation will be performed at each visit sequentially, using a regression method obtained from BSC alone patients with terms for baseline score, the randomization stratification variable, and previous visits. After obtaining complete data sets for each visit, these complete data sets will be analyzed using MMRM analysis, and inferences from each complete data set will be combined to obtain an overall test statistic for treatment effect. The basic SAS code for this is:

```
Proc mi data=adefft out=monotone seed=1306528 nimpute=pctmissing;
  by trt01p;
  mcmc impute=monotone;
  var intubn base Day5 Day10 Day15 Day22 Day29;
run;
```

where trt01p is a variable that indicates the patient's randomized treatment group, base is the value at baseline, Day5 – Day29 are the changes from baseline at a particular visit, and intubn is a dummy variable for the randomization stratification factor.

The following is a partial SAS code for the BSC alone-based imputation at Day X:

```
Proc mi data=monotone out=outmi seed=1306539 nimpute=1;
  by _imputation_;
  class trt01p intub;
```

```
var intub base Day5 Day10 Day15 Day22 Day29;  
monotone reg(Day X = intub base prev_DayX(s) / details);  
mnar model (Day X / modelobs=(trt01p='BSC'));  
  
run;
```

The imputed data sets are then analyzed using MMRM by imputation as described above and the PROC MIANALYZE procedure will be used to generate valid statistical inferences about these parameters. The basic SAS code for this is:

```
Proc mianalyze data=diffs;  
    by avisit;  
    modeffects estimate;  
    stderr stderr;  
  
run;
```
